2.0 Other TAVI Related Complications

Complication	Definition
Conversion to open surgery	Conversion to open sternotomy during the TAVI procedure secondary to any
	procedure-related complications
Unplanned use of	Unplanned use of CPB for hemodynamic support at any time during the TAVI
cardiopulmonary bypass	procedure
Coronary artery obstruction	Angiographic or echocardiographic evidence of a new, partial or complete,
	obstruction of a coronary ostium, either by the CoreValve™ Evolut™ PRO
	prosthesis itself, the native leaflets, calcifications, or dissection, occurring
	during or after the TAVI procedure.
Ventricular septal perforation	Angiographic or echocardiographic evidence of a new septal perforation
	during or after the TAVI procedure
Mitral valve apparatus damage or	Angiographic or echocardiographic evidence of new damage (chordae,
dysfunction	papillary muscle, or leaflet) to the mitral valve apparatus or dysfunction (e.g.,
	restrictions due to the CoreValve™ Evolut™ PRO) of the mitral valve during or
	after the TAVI procedure
Cardiac tamponade	Evidence of new pericardial effusion associated with hemodynamic instability
	and clearly related to the TAVI procedure
Prosthetic valve thrombosis	Any thrombus attached to or near an implanted valve that occludes part of
	the blood flow path, interferes with valve function, or is sufficiently large to
	warrant treatment.
	*Valve-associated thrombus identified at autopsy in a patient whose cause of
	death was not valve related should not be reported as valve thrombosis.
Valve migration	After initial correct positioning, any observed movement (upward or
	downward) of the Evolut PRO within the aortic annulus from its initial
	position, with or without consequences.
Valve embolization	The Evolut PRO moves during or after deployment such that it loses contact
	within the aortic annulus
	Note: Valve embolizations are not applicable to valve that move during the
	procedure but are able to be recaptured and repositioned.
Ectopic valve deployment	Permanent deployment of the Evolut PRO in a location other than the aortic
	root
TAV in TAV deployment	Additional valve prosthesis is implanted within a previously implanted
	CoreValve™ Evolut™ PRO because of sub-optimal device position and/or
	function, during or after the index procedure.
	Note: TAV in TAV deployment is not a reintervention as it captures valve in
	valve deployment during the index procedure and Percutaneous
	Reintervention – TAV in TAV Deployment captures valve in valve deployment
	after the index procedure.
Hemolysis	Red cell destruction as evidenced by plasma free hemoglobin >50 mg/dl
	Minor hemolysis: No intervention required
	Major hemolysis: Requires intervention (e.g., iron supplements, transfusion,
	invasive intervention).

MDT18065EVR009 Version 5.0 06-Oct-2023 Page 107 of 121

Complication	Definition
Frame fracture	Visual evidence on radiography or at explant of loss of contact between
	elements (cells) of the stent.
	Minor frame fracture: Does not require intervention or is not associated with
	prosthetic valve dysfunction.
	Major frame fracture: Intervention required (e.g., reoperation, catheter re-
	intervention) or is associated with prosthetic valve dysfunction
Valve Thrombosis (Sub-Clinical)	Any thrombus not caused by infection attached to or near the trial valve
	that occludes part of the blood flow path or interferes with valve function,
	without evident clinical sequelae, causing a hemodynamic impediment
	meeting the following criteria:
	 Increase in aortic regurgitation to moderate to severe.
	An increase by more than 50% of discharge mean aortic valve gradient (with
	the post discharge mean gradient being ≥ 20 mmHg) or a decrease in the
	Doppler Velocity Index (DVI) by more than 50%
Leaflet Motion Abnormality (With	Possible leaflet motion abnormality identified by any imaging modality with
Treatment)	medical therapy (e.g., anticoagulation therapy, fibrinolytic therapy or valve-
· ·	related medical intervention) initiated and without significant negative
	change in valve function (i.e. increasing obstruction or central regurgitation).
Leaflet Motion Abnormality	Possible leaflet motion abnormality identified by any imaging modality
(Without Treatment)	without medical therapy (e.g., anticoagulation therapy, fibrinolytic therapy or
	valve-related medical intervention) initiated but without significant negative
	change in valve function (i.e. increasing obstruction or central regurgitation).
TAVR Conversion to Other	Any conversion of the intended TAVR procedure, prior to closure to other
Percutaneous Procedure	percutaneous intervention due to technical challenges, technical
	contraindications to the intended procedure identified intra-procedurally or
	complications.
Aborted Procedure	Termination of the procedure prior to implantation of the valve due to
	identification of a technical contraindication, intraprocedural complications of
	a concomitant procedure prior to valve implantation or radiation dosage.
Reintervention – Surgical or	Any surgical or percutaneous interventional catheter procedure that repairs,
Percutaneous	otherwise alters or adjusts, or replaces a previously implanted valve. In
	addition to surgical reoperations, balloon dilatation, interventional
	manipulation, repositioning, or retrieval, and other catheter-based
	interventions for valve-related complications are also considered
	reinterventions. Reintervention is further subdivided into surgical and
	percutaneous.

PROSTHETIC VALVE ENDOCARDITIS

Any of the following:

1) Fulfillment of the following Duke criteria⁴² for definite endocarditis:

MDT18065EVR009 Version 5.0 06-Oct-2023 Page 108 of 121

Medtronic

PROSTHETIC VALVE ENDOCARDITIS

- Histologic and/or microbiologic evidence of infection at surgery or autopsy, or
- 2 major criteria, or
- 1 major criteria and 3 minor criteria, or
- 5 minor criteria

Major and minor criteria are as follows:

Major Criteria:

- Blood cultures positive for Infective Endocarditis (IE)
 - Typical microorganisms consistent with IE isolated from two separate blood cultures, as noted below
 - Viridans streptococci, Streptococcus bovis, Staphylcoccus aureus, or HACEK group
 - Community-acquired enterococci in the presence of a primary focus
 - Microorganisms consistent with IE isolated from persistently positive blood cultures defined as:
 - At least two positive cultures or blood samples obtained >12 hours apart, or
 - All of three, or a majority of four or more separate cultures of blood, the first and last sample obtained > one hour apart
 - Single blood culture positive for Coxiella burnetti or an antiphase I IG antibody titer >1:800
- Evidence of endocardial involvement
 - Positive results of echocardiography for IE defined as:
 - Oscillating intracardiac mass on a valve or supporting structures in the path of regurgitant jets or on implanted material in the absence of an anatomic explantation, or
 - Abscess, or
 - New partial dehiscence of a valvular prosthesis
 - New valvular regurgitation (worsening or changing or pre-existing murmur not sufficient)

Minor Criteria:

- Predisposition: predisposing heart condition or intravenous drug use
- **Fever:** temperature >38°C
- Vascular phenomena: major arterial emboli, septic pulmonary infarcts, mycotic aneurysm, intracranial hemorrhage, conjunctival hemorrhages, and Janeway's lesions
- Immunological phenomena: glomerulonephritis, Osler's nodes, Roth's spots, and rheumatoid factor
- **Microbiological evidence:** positive blood culture but does not meet a major criterion (as noted above) or serological evidence of active infection with organism consistent with infectious endocarditis.
- Echocardiographic findings: consistent with IE but do not meet a major criterion as noted above

If only 1 major and 1-2 minor criteria are fulfilled, or if only 3-4 minor criteria are fulfilled, the event will be coded as "possible endocarditis"

- 2) Evidence of abscess, paravalvular leak, pus, or vegetation confirmed as secondary to infection by histological or bacteriological studies during a re-operation
- 3) Findings of abscess, pus, or vegetation involving the CoreValve™ Evolut™ PRO at autopsy

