26.1. Clinical Events Committee

A Clinical Events Committee (CEC) will provide independent medical review and adjudication of adverse event data used in the endpoint assessment of the investigational device. The CEC will adjudicate all deaths, and all endpoint related events reported by the investigators. The analysis of the study endpoint data will be based on CEC adjudicated events. Endpoint definitions are provided in APPENDIX V: DEFINITIONS: SAFETY ENDPOINTS AND EFFICACY EVENTS.

The CEC members will be free from bias towards the study and will be independent from both the study and investigators and Medtronic. The committee will consist of at least 3 independent experts (non-Medtronic employed physicians) with expertise relevant to the study. This may include experience in the areas of:

- Cardiac surgery
- Interventional cardiology
- Neurology
- Electrophysiology

A CEC charter will be established that describes the Committee roles, responsibilities, and processes.

27. Appendices

- I.Names and Addresses of Investigational Centers
- **II.Echocardiography Procedures**
- III. MDCT Acquisition Guidelines
- IV. STS Calculator and Risk Factors
- V. Definitions: Safety Endpoints and Efficacy Events
- VI.Study contacts
- VII. Sample informed consent form

MDT18065EVR009 Version 5.0 06-Oct-2023 Page 79 of 121 Medtronic

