#### 7. Prosthetic valve endocarditis at 30 days, 6 months, one year, and annually through 5 years

Event rate estimates will be provided at 30 days, 6 months, 1 year and annually through 5 years for the attempted implant set. The outcome is descriptive including Kaplan-Meier rates and no statistical hypothesis test is specified.

Revision 3.0

Page 22 of 23

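### The endocarditis definition makes community-acquired enterococcal cultures a major criterion when another infection source is present; the condition looks reversed and should be checked against the cited Duke reference (minor)

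*Protocol*

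**What the plan says.** The blood-culture major criterion in Appendix V, 2.0 (Prosthetic Valve Endocarditis) has two routes relevant here.

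- **Typical organism:** "Typical microorganisms consistent with IE isolated from two separate blood cultures, as noted below". Viridans streptococci, *S. bovis*, *S. aureus* and the HACEK group carry no condition about another source. Enterococci carry one: "Community-acquired enterococci in the presence of a primary focus".
- **Persistent positivity:** "Microorganisms consistent with IE isolated from persistently positive blood cultures defined as" one of two patterns. The first is "At least two positive cultures or blood samples obtained >12 hours apart, or" the second, which is all of three cultures, or a majority of four or more, with the first and last over an hour apart. Neither pattern mentions a focus.

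A positive culture that misses the major criterion scores as one minor criterion. Definite endocarditis needs 2 major, 1 major plus 3 minor, or 5 minor criteria, or histological or microbiological evidence at surgery or autopsy. A lower category, possible endocarditis, takes cases that fall short: "If only 1 major and 1-2 minor criteria are fulfilled, or if only 3-4 minor criteria are fulfilled, the event will be coded as" belonging to that category.

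The echo major criterion in the same block accepts an oscillating mass "on implanted material in the absence of an anatomic explantation", where the last word is evidently meant to be *explanation*.

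SAP 7.10.5, item 7, covers "Prosthetic valve endocarditis at 30 days, 6 months, one year, and annually through 5 years", reported as descriptive Kaplan-Meier rates in the attempted implant set. Protocol 26.1 refers to Appendix V for endpoint definitions and adds: "The analysis of the study endpoint data will be based on CEC adjudicated events".

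**The concern.** A criterion headed as blood cultures positive for infective endocarditis should pick out bacteraemia that points to the valve. A primary focus elsewhere is a competing explanation. Under this line the competing explanation strengthens the case for valve infection, and its absence weakens it. No rationale is given, and the neighbouring echo criterion works the other way round.

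If the line is followed literally, a case without a source can be coded possible while a case already explained elsewhere is coded definite. The outcome is rare and the cohort small, so one case is visible in the reported rate. The last implant was in February 2023 and follow-up runs to 5 years, so most of the reporting is still ahead.

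**Working it through.** The documents give no endocarditis rate to reproduce, so the check applies the scoring rules as written.

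**Setting.** Community-acquired enterococcus in two separate cultures that meet neither persistence pattern. The prosthetic valve is counted as the predisposition minor criterion (an assumption). The surgical, re-operation and autopsy routes are left out because they do not depend on the blood-culture score.

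**Patterns.** Echo finding (major, minor, none) × fever × vascular × immunological = 3 × 2 × 2 × 2 = 24. Let *k* be how many of fever, vascular and immunological are present. The values *k* = 0, 1, 2, 3 cover 1, 3, 3 and 1 patterns per echo state.

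| Echo | Culture scores as | Tally | k=0 | k=1 | k=2 | k=3 |
|---|---|---|---|---|---|---|
| major | minor | 1 major, 2+k minor | possible | definite | definite | definite |
| major | major | 2 major | definite | definite | definite | definite |
| minor | minor | 3+k minor | possible | possible | definite | definite |
| minor | major | 1 major, 2+k minor | possible | definite | definite | definite |
| none | minor | 2+k minor | neither | possible | possible | definite |
| none | major | 1 major, 1+k minor | possible | possible | definite | definite |

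**Switches between possible and definite:** echo major with k=0 (1), echo minor with k=1 (3), no echo finding with k=2 (3). Total 1 + 3 + 3 = 7 of 24. One further pattern (no echo finding, k=0) switches between neither and possible.

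- *No focus:* the culture is minor as written. Definite in 7 + 4 + 1 = 12 of 24; with the condition reversed, 8 + 7 + 4 = 19.
- *Focus present:* the mirror image, 19 as written and 12 reversed.
- *Persistent cultures:* no pattern changes.
- *Predisposition allowed to be absent as well:* 15 of 48 patterns switch between possible and definite.

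**Two concrete cases**, both with the culture setting above:

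1. No source found, fever, arterial embolus: predisposition + fever + vascular + microbiological = 4 minor, so possible. Reversed: 1 major + 3 minor, so definite.
2. Urinary source found, fever, conjunctival haemorrhage: 1 major + 3 minor (predisposition, fever, vascular), so definite. Reversed: 4 minor, so possible.

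**Effect on the rate**, with n = 50 (Protocol 10.2.1), no censoring, and only definite cases counted. One subject is 1/50 = 2.0 points. Using the log-log Greenwood interval of SAP 7.2.2 for one event: S = 0.98; SE = √(1/(50×49)) / |ln 0.98| = 0.0202/0.0202 = 1.00; limits 1 − 0.98^exp(∓1.96) = 0.28% and 13.4%. For two events: 4.0% (1.0% to 15.1%). With no events the log-log interval is undefined; the exact interval is 0 to 7.1%. The number of affected subjects is unknown; 0, 1 and 2 are shown as an assumed range.

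**The case against.** The strongest objection is that the documents never state the right wording. The Duke reference is cited but not reproduced, and the internal support is an analogy with the echo criterion, whose own wording needs a correction to make sense. This stands as far as the remedy goes: the documents justify checking the line and expecting it to be reversed, not changing it unchecked. The version 5.0 change log records a typo correction in the endocarditis definition without saying which, so it does not settle the matter.

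A reader might also infer more than the text supports:

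- *That enterococci count only with a focus.* They do not. Either persistence pattern meets the major criterion without one, including cultures all drawn within 12 hours if all of three, or a majority of four or more, are positive. Enterococci that are not community-acquired are outside the line altogether.
- *That source-less cases generally drop to possible.* In 12 of the 24 no-focus patterns the case is definite anyway.
- *That a focus makes a case definite.* It supplies at most one major criterion; a second major or three minor criteria are still needed.
- *That the 5-year rate will be wrong.* Neither document says whether possible cases enter it. The first limb of the definition opens with criteria for definite endocarditis, which suggests they do not, but that is not a counting rule.

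The adjudication path is also less explicit than it first appears. Endocarditis sits under other TAVI-related complications rather than safety endpoint definitions, and SAP 7.10.5, item 7, does not mention the Clinical Events Committee (CEC). Protocol 26.1 and SAP 7.11 are broad enough to cover it but do not name it.

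These points limit how often the line matters. They do not explain why a competing source should raise the score.

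**Conclusion.** The line is wrong on its face and can misclassify in both directions, but within a small area; severity is minor. For non-persistent, community-acquired enterococcal bacteraemia in a prosthetic-valve subject, 7 of 24 criterion patterns change between possible and definite. These are counts of patterns, not probabilities. The 2 points per reclassified subject rest on only definite cases being events and on no censoring among the 50. The affected number may well be zero. The outcome is one of 13 descriptive other outcome measures, without a hypothesis test. That the condition should read *absence* is inferred from the structure of the definition and awaits confirmation from the cited source.

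**What to change.** 1. Check the enterococcal line in Appendix V, 2.0, against protocol reference 42. If the check confirms the reversal, change *presence* to *absence*; correct *explantation* to *explanation* in the echo criterion at the same time.
2. State in SAP 7.10.5, item 7, whether cases coded possible enter the Kaplan-Meier rate, and whether the item uses CEC-adjudicated events.
3. Send the corrected definition to the CEC, and re-check any community-acquired enterococcal bacteraemia already classified before the next endocarditis rate is reported.

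The cost is a small text amendment, one or two sentences in the SAP, and re-review of at most a handful of records. No new data or visits are needed.

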3.0 Efficacy Event Definitions

PROSTHETIC VALVE DYSFUNCTION	
Stenosis: moderate/severe	
	Any of the following
	1) Peak aortic velocity >4 m/s OR mean aortic gradient >40 mmHg, AND EOA <0.8 cm ² .

MDT18065EVR009 Version 5.0 06-Oct-2023 Page 109 of 121

PROSTHETIC VALVE DYSFUNCTION		
	2) Peak aortic velocity >4 m/s OR mean aortic gradient >40 mmHg, AND EOA ≥0.8 cm², and DVI <0.25,	
	3) Peak aortic velocity ≤ 4 m/s and mean aortic gradient ≤ 40 mmHg, AND EOA < 0.8 cm ² , and DVI < 0.25	
Paravalvular regurgitation: moderate	Moderate paravalvular regurgitation (per echo criteria in CIP, Table 8)	
Paravalvular regurgitation: severe	Severe paravalvular regurgitation (per echo criteria in CIP, Table 8)	
Transvalvular regurgitation: moderate	Moderate transvalvular regurgitation (per echo criteria in CIP, Table 8)	
Transvalvular regurgitation: severe	Moderate or severe transvalvular regurgitation (per echo criteria in CIP, Table 8)	
Total regurgitation: moderate	Moderate total regurgitation (per echo criteria in CIP, Table 8)	
Total regurgitation: severe	Severe total regurgitation (per echo in CIP, Table 8)	

Notes:

- 1. DVI = Doppler Velocity Index (LVOT VTI/valve VTI)
- 2. For subjects with BSA <1.6 m², the EOA criteria for significant (moderate or severe) stenosis is <0.6 cm²
- 3. For subjects LVOT diameter >2.5 cm, the DVI criteria for significant (moderate or severe) stenosis is 0.2
- 4. Reporting of prosthetic valve dysfunction will be based on echo (if available).
- 5. Prosthetic valve dysfunction events are not reported as adverse events, unless the dysfunction is accompanied with clinical sequelae at the time of event detection, and the clinical sequelae are chronologically and physiologically associated with the dysfunction. However, prosthetic dysfunctions that are associated with adverse events, and that meet the definition of a serious adverse event, should be reported as such.

MDT18065EVR009 Version 5.006-Oct-2023 Page 110 of 121

Classification of Causal Relationships 4.0

The following definitions are intended as guidelines for classifying causal relationships between the event and the TAV, the delivery catheter system, and the TAVR implant procedure. Timeframe for assessing implant procedure relationships begins when the subject is being prepared for the TAVR implant (or re-implant) procedure.

Causai relationships be	tween event and the TAV	
Not related to the TAV	 The relationship to TAV can be excluded when: the event is not a known side effect of the TAV product category the device belongs to or of similar devices; The event has no temporal relationship with the TAV The event does not follow a known response pattern to the TAV is biologically implausible; The event involves a body-site or an organ not expected In order to establish non-relatedness, not all the criteria listed above might be met at the same time. 	
Unlikely to be related to the TAV	The relationship with the TAV seems not relevant and/or the event can be reasonably explained by another cause, but additional information may be obtained.	
Possibly related to the TAV	The relationship with the TAV is weak but cannot be ruled out completely. Alternative causes are also possible (e.g., an underlying or concurrent illness/ clinical condition or/and an effect of another device, drug or treatment). Cases where relatedness cannot be assessed or no information has been obtained should also be classified as possible.	
Probably related to the TAV	The relationship with TAV seems relevant and/or the event cannot reasonably be explained by another cause, but additional information may be obtained.	
Causal relationship "Related" to the TAV	 The event is associated with the TAV beyond reasonable doubt when: the event is a known side effect of the TAV product category the device belongs to or of similar devices; the event has a temporal relationship with investigational device use/application or procedures; the event involves a body-site or organ that the TAV or surgical valve is applied to; the TAV of surgical valve has an effect on; the event follows a known response pattern to the TAV; other possible causes (e.g., an underlying or concurrent illness/clinical condition or an effect of another device, drug, or treatment) have been adequately ruled out harm to the subject is due to error in use In order to establish relatedness, not all the criteria listed above might be met at the same time. 	

MDT18065EVR009 Version 5.006-Oct-2023 Page

Page 111 of 121

Causal relationships between event and the TAVR delivery system

en event and the TAVR delivery system	
 The relationship with the TAVR delivery system can be excluded when: the event is not a known side effect of the TAVR delivery system product category the device belongs to or of similar devices; The event has no temporal relationship with the use of the TAVR delivery system The event does not follow a known response pattern to the TAVR delivery system and is biologically implausible; The event involves a body-site or an organ not expected In order to establish non-relatedness, not all the criteria listed above might be met at the same time 	
The relationship with the TAVR delivery system seems not relevant and/or the event can be reasonably explained by another cause, but additional information may be obtained.	
The relationship with the TAVR delivery system is weak but cannot be ruled out completely. Alternative causes are also possible (e.g., an underlying or concurrent illness/ clinical condition or/and an effect of another device, drug or treatment). Cases were relatedness cannot be assessed or no information has been obtained should also be classified as possible.	
The relationship with the TAVR delivery system seems relevant and/or the event cannot reasonably be explained by another cause, but additional information may be obtained.	
 The event is associated with the TAVR delivery system reasonable beyond doubt when: the event is a known side effect of the product category the device belongs to or of similar devices; the event has a temporal relationship with the TAVR delivery system use/application; the event involves a body-site or organ that the TAVR delivery system is applied to; the TAVR delivery system has an effect on; the event follows a known response pattern to the TAVR delivery system; other possible causes (e.g., an underlying or concurrent illness/clinical condition or an effect of another device, drug, or treatment) have been adequately ruled out harm to the subject is due to error in use In order to establish relatedness, not all the criteria listed above might be met at the same time.	

MDT18065EVR009

Version 5.006-Oct-2023

Page 112 of 121

Causal relationships between event and the TAVR implant procedure

Caasa Telationsiips Settie	en event and the TAVK implant procedure	
Not related to the TAVR	The relationship with the TAVR implant procedure can be excluded when:	
implant procedure	the event is not a known side effect of the TAVR implant procedure;	
	The event has no temporal relationship with the TAVR implant relationship	
	The event does not follow a known response pattern to the TAVR implant procedure and is biologically implausible;	
	The event involves a body-site or an organ not expected	
	In order to establish non-relatedness, not all the criteria listed above might be met at the same time.	
Unlikely to be related to the TAVR implant procedure	The relationship with the TAVR implant procedure seems not relevant and/or the event can be reasonably explained by another cause, but additional information may be obtained.	
Possibly related to the TAVR implant procedure	The relationship with the TAVR implant procedure is weak but cannot be ruled out completely. Alternative causes are also possible (e.g., an underlying or concurrent illness/ clinical condition or/and an effect of another device, drug or treatment). Cases were relatedness cannot be assessed or no information has been obtained should also be classified as possible.	
Probably related to the TAVR implant procedure	The relationship with TAVR implant procedure seems relevant and/or the event cannot reasonably be explained by another cause, but additional information may be obtained.	
Causal relationship "Related" to the TAVR	The event is associated with the TAVR implant procedure beyond reasonable doubt when:	
delivery system	the event is a known side effect of the TAVR implant procedure;	
	 the event has a temporal relationship with the TAVR implant procedure; the event involves a body-site or organ that 	
	o the TAVR is applied to;	
	 the TAVR implant procedure has an effect on; the event follows a known response pattern to the TAVR implant 	
	procedure;	
	other possible causes (e.g., an underlying or concurrent illness/clinical condition or an effect of another device, drug, or treatment) have been adequately ruled out	
	harm to the subject is due to error in use	
	In order to establish relatedness, not all the criteria listed above might be met at the same time.	

[figure not shown]
Note: Procedure related events refer to the procedure related to the initial application of the investigational medical device only and therefore not to any other procedures or treatments applied later throughout the clinical investigation, for instance to treat (serious) adverse events.

MDT18065EVR009 Version 5.0 06-Oct-2023

Page 113 of 121

